3.4 Duration of Study Participation

The expected study participation is approximately 10 years after AT132 administration; approximately 12 years for control subjects who are ultimately administered AT132 (at least 24 weeks to 3 years delayed treatment and an additional 10 years after AT132 administration).

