- ^o Platelet monitoring: Peripheral blood smears should be performed as part of the hematology panel. Platelet monitoring consists of the following tests: Platelet Activation Assays (CD62P, Activated GP IIb/IIIa w/ PAC-1, and Phosphatidylserine), Reticulated Platelets, Platelet Circulating Antibodies. For EU sites ONLY: Reticulated platelets will be tested locally. Sample for platelet activation assays must be fixated locally prior to shipping.
- ^p IFN- γ ELISpot: Following AT132 administration, in cases of clinically important elevated bilirubin, elevated aminotransferases, elevated troponins, and/or elevated creatine phosphokinase that in the Investigator's judgment may be related to T-cell responses, repeat IFN- γ ELISpot response testing is suggested. Appropriate care for an individual subject will be determined by the Investigator based on an assessment of the subject's overall medical status.
- ^q Footnote was deleted.
- ^r For control subjects whose wrist X-ray was within the past 6 months, this does not need to be repeated at their second baseline assessment before treatment with AT132. Subjects in Germany will not have a wrist X-ray.
- ^s The diary should be completed daily by the same parent/LAR/caregiver (whenever possible); see [Section 5.1.1.11.2.1](#).
- ^t If a subject has discontinued the use of the ventilator and has 2 assessments with the MIP at 80 cmH₂O, testing for MIP, MEP, and P0.1 will not be required for future visits.
- ^u The site pulmonologist and local pulmonologist, if applicable, will review the results from the visit, assess the subject, determine if the subject meets the criteria outlined in [Table 1](#) to begin reduction of hours on the ventilator, and determine if the subject meets the criteria outlined in [Table 2](#) to discontinue the ventilator.
- ^v The severity of secretions and burden of secretions management will be assessed using the PGIS-S and PGIS-I ([Appendix 3](#)). The same parent/LAR/caregiver should report throughout the study (whenever possible).
- ^w At baseline, the PGIS-S is conducted for all subjects. At baseline, the PGIS-I is conducted only for control subjects who are attending their second baseline assessments before treatment with AT132 (whenever possible).
- ^x All physical therapy assessments should be videoed and performed according to the site manual.
- ^y If a subject has a total score of 56 for 2 consecutive assessments, the CHOP INTEND will not be required for future visits.

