- ^m The severity of secretions and burden of secretions management will be assessed using the PGIS-S and PGIS-I ([Appendix 3](#)). The same parent/LAR/caregiver should report throughout the study (whenever possible).
- ⁿ At baseline, the PGIS-S is conducted for all subjects.
- ^o All physical therapy assessments should be videoed and performed according to the site manual.
- ^p The PedsQL is to be performed for all subjects, regardless of age. Subjects < 2 years of age should be administered the version for 2- to 4-year-olds.
- ^q See [Appendix 5](#). At baseline, only the CGI-S is conducted for all subjects.
- ^r Parents/LARs/caregivers (the same person every time, whenever possible) in ASPIRO will be asked to complete forms for subjects 8 months and older.

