Appendix 3: Secretions Management Assessment: PGIS-S and PGIS-I

Parental Global Impression of Secretion Severity (PGIS-S)

Taking into consideration the experience and understanding you have of your child; in terms of secretion management (ie, volume and thickness of secretions, and how often you need to suction your child) – how affected has your child been over the past 7 days?

- 1 – not affected
- 2 – borderline affected
- 3 – mildly affected
- 4 – moderately affected
- 5 – markedly affected
- 6 – severely affected
- 7 – among the worst he has ever been

Parental Global Impression of Secretion Improvement (PGIS-I)

In comparison to the baseline assessment (ie, the start of the study), and specifically with regard to management of secretions (ie, volume, thickness, frequency of suctioning), how has he changed?

- 1 – very much improved
- 2 – much improved
- 3 – minimally improved
- 4 – no change
- 5 – minimally worse
- 6 – much worse
- 7 – very much worse

Name of parent/LAR/caregiver providing information: _____

Date of completion: _____

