4.5.1.2.5 Change from baseline in the proportion of participants being able to feed without a gastrostomy or G-tube at Week 24

A participant’s ability to feed without a gastrostomy tube (G-tube) is evaluated by the Parental Swallowing Questionnaire. A participant score of “Never (0)” on the first item of the

questionnaire, “Since the last visit how often do you use the following with your child – Tube Feeding” will indicate that the participant met the criteria in the endpoint at the visit.

A shift table of the number and proportion of participants meeting the criteria described above will be presented by dose level. The shift from baseline G-tube status to best post-baseline G-tube status will be summarized, as well as the shifts to each visit.

4.5.1.2.6 Change from baseline in the Communicative Development Inventories scores at Week 24

The Communicative Development Inventories scores and corresponding change from baseline at each visit will be summarized descriptively by dose level group.

CDI scores for each participant will be calculated as number of items marked by caregiver/ number of items on questionnaire. This is a raw, unadjusted score.

4.5.1.2.7 Change from baseline in the Parental Global Impression of Secretion Severity (PGIS-S) score at Week 24

The PGIS-S scores and corresponding change from baseline at each visit will be summarized descriptively by dose level group.

Parents/LAR/caregiver will report on the amount of suctioning and secretions management required over the previous week, using a scale of 1 to 7 (1 = not affected and 7 = among the worst he has ever been) to report impression of change from baseline and impression of current severity.

Missing values will not be imputed.

4.5.1.2.8 Change in the Parental Global Impression of Secretion Improvement (PGIS-I) score at Week 24

The PGIS-I scores at each visit will be summarized descriptively by dose level group.

Parents/LAR/caregiver will report on the amount of suctioning and secretions management required over the previous week, using a scale of 1 to 7 (1=very much improved and 7 = very much worse) to report impression of change from baseline.

Missing values will not be imputed.

4.5.1.2.9 Change from baseline in Clinical Global Impression of Severity (CGI-S) at Week 24

The CGI-S scores and corresponding change from baseline at each visit will be summarized descriptively by dose level group.

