4.10 Additional Conventions

4.10.1 Baseline Definition

Unless otherwise specified, baseline is defined as the last assessment collected in ASPIRO study prior to time/date of dosing with study drug.

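### PGIS-I asks about change since the study began, so for delayed-treatment controls dosed later the post-dose score may include untreated time, yet the SAP pools it by dose

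*SAP*

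**What the plan says.** - **The question put to the parent** (Protocol Appendix 3, PGIS-I): "In comparison to the baseline assessment (ie, the start of the study), and specifically with regard to management of secretions", scored from 1 (best) to 7 (worst).
- **When it is asked.** For treated children, Protocol 5.4 footnote w: "At baseline, the PGIS-I is conducted only for control subjects who are attending their second baseline assessments before treatment with AT132 (whenever possible"). At the control baseline (Protocol 5.7 footnote n) only the PGIS-S is mentioned. Later control visits list the secretions assessment, which footnote m says uses both scales.
- **How long controls wait** (Protocol 3.4): "at least 24 weeks to 3 years delayed treatment".
- **How it is analysed** (SAP 4.5.1.2.8): "The PGIS-I scores at each visit will be summarized descriptively by dose level group". The same section describes the scale as an impression of change from baseline.
- **What baseline means in the SAP** (4.10.1), unless otherwise specified: "baseline is defined as the last assessment collected in ASPIRO study prior to time/date of dosing with study drug".
- **Who is included.** Exploratory endpoints use the FAS (SAP 4.5), which takes in every dosed child with a post-dose efficacy assessment (SAP 3). Grouping is by dose received, and only the two never-dosed controls are left out (SAP 1.3). No subgroup analyses are planned (SAP 4.7.2).

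**The concern.** For most endpoints the SAP's pre-dose baseline puts former controls and immediately treated children on the same footing, because change is computed by subtraction. PGIS-I is different. The parent supplies the change, measured from whatever starting point the form gives, and no choice of baseline record in the SAP can alter that.

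Taken literally, the form's starting point coincides with the SAP baseline for a child dosed without a control period. It does not for a child who first spent months as a control. A by-dose table would then combine ratings over different periods under one label, and a reader would naturally take it as change since AT132. The groups are small, so a few children with a different recall period could visibly shift a distribution. It would also sit awkwardly with the SAP version history (version 3.0, study design row), which says that control-period data will not be used: the untreated period would come back in through the parent's recall.

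**Working it through.** The plan gives no figure on this point, so the check is a comparison of texts followed by simple arithmetic.

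**1. Literal anchor for a former control.** Such a child has two baselines: the control baseline and the pre-dose baseline. The form's gloss points to the first. Between the two, parents answer PGIS-I at control visits, necessarily against the control baseline. After dosing they receive the same form. Neither document tells them to move the reference.

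**2. Recall period at post-dose Week 24.** Recall = wait + 24 weeks; untreated share = wait / (wait + 24).

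| Wait before dosing | Recall at Week 24 | Untreated share |
|---|---|---|
| None (dosed directly) | 24 weeks | 0% |
| 24 weeks (minimum) | 24 + 24 = 48 weeks | 24/48 = 50% |
| 3 years (upper bound): 3 × 365.25/7 = 156.5 weeks | 156.5 + 24 = 180.5 weeks | 156.5/180.5 = 87% |

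The last row is a planning bound, not an observed wait. Part 2 controls dosed before protocol v8 were to be treated after their Week 24 data, so about 50% is the design figure for them.

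**3. How many children.** The documents do not tabulate this. An inference from their numbers:
- Part 1: 6 treated + 1 control in Cohort 1, and 3 + 5 treated + 1 control in Cohort 2 (5 being the top of the 3-to-5 expansion in Protocol 1.4.2). Total 7 + 9 = 16, the planned Part 1 number.
- Part 2: 10 children at 1:1 gives 5 controls. Three were undosed at v8, so 5 − 3 = 2 had been dosed.
- High dose: 8 (Cohort 2) + 2 (Part 1 controls) + 5 (Part 2 treated) + 2 (Part 2 controls) = 17, matching the 17 in Protocol 1.4.2. Former controls: 2 + 2 = 4, and 4/17 = 24%.
- Low dose: two of the three remaining controls were never dosed (SAP 1.3), so 3 − 2 = 1 was. That gives 6 + 1 = 7, and 1/7 = 14%.

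Because this is inferred, a range is fairer: 1 to 5 former controls among 17 is 6% to 29%; 0 or 1 among 7 is 0% to 14%.

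**4. How many have a Week 24 rating.** Unknown. Four treated children died, one of them at the low dose (Protocol 1.5). Death dates are not given, and missing PGIS-I values are not imputed (SAP 4.5.1.2.8).

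**5. A side effect in the visit table.** SAP Table 9, column (b), gives PGIS-I a baseline window. Under footnote w only former controls can fill it, so a baseline row would describe different children from the rows below it.

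**The case against.** The strongest reply is that the anchor is open. Protocol 6.1.3 distinguishes a Control Baseline from the Baseline before dosing, and Protocol 5.3 restarts former controls on the treated schedule at the Biopsy and Baseline Visits. A parent could take the form's baseline assessment to be that second one. This stands in part: the documents show an unreset literal anchor, not which anchor each parent used. That uncertainty does not make silent pooling safe.

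A reader might go further and infer that footnote w proves the post-dose anchor is the control baseline. It does not. It shows only that a rating given before dosing must look back to the control baseline, and it could serve simply to close the control period. CGI-I is likewise given at the second baseline to controls only (footnote aa), although its form refers to Study Day 1. That parallel weakens footnote w as evidence, but it does not rescue the plan, because the control schedule in Protocol 5.7 has its own study-day count.

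Three further points stand. The second-baseline PGIS-I was to be collected only where possible, so some values may be missing. PGIS-S change from the pre-dose baseline is already planned (SAP 4.5.1.2.7). And the endpoint is exploratory, with no hypothesis testing (SAP 2), so only interpretation is affected.

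**Conclusion.** The point holds as a small, cheaply mended weakness. As worded, PGIS-I may carry untreated change for former controls: about half of the recall period at post-dose Week 24 after a 24-week wait, and a larger share after longer waits. SAP 4.5.1.2.8 pools those scores with the rest.

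This assumes that parents follow the form's gloss. The counts of about 4 of 17 and 1 of 7 assume that enrolment followed the planned numbers, and not all of these children may have a Week 24 rating.

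A reader might infer that untreated change is being credited to the drug. The documents do not support that: the SAP does not present PGIS-I as a drug effect, and secretions during the wait could have improved or worsened, so the direction of any bias is unknown.

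**What to change.** In SAP 4.5.1.2.8:
- Base the by-dose PGIS-I summary on children dosed without a control period.
- Show former controls separately, or flagged, with the second-baseline PGIS-I beside the post-dose value where it was collected.
- State the form's reference point in a table footnote.

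In SAP 4.5.1.2.7, state that PGIS-S change from the pre-dose baseline is the secretion measure that can be pooled across all dosed children. That form asks about the past 7 days, so it has no recall-anchor problem.

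The cost is SAP and table wording, with no new data. The pooled PGIS-I groups shrink slightly: on the inferred counts, from 17 to 13 at the high dose and from 7 to 6 at the low dose. The side-by-side display will have gaps where the second-baseline rating was not obtained. The SAP should say that this is a presentation split for one exploratory table, so that it does not appear to conflict with the FAS rule or the absence of subgroup analyses.

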4.6 Safety Analyses

The safety endpoints for this study are the following:

Adverse events (AEs), serious AEs (SAEs), and findings from safety laboratory tests, 12-lead electrocardiogram (ECG), echocardiograms (ECHOs), vital signs, growth parameters, physical examinations, liver ultrasounds, antibody formation (anti AAV8, anti MTM1), viral shedding, annualized hospitalization rate, annualized respiratory and non-respiratory SAE rate, and length of stay per hospitalization.

Safety analysis will be conducted for the SAF, unless specified otherwise.

4.6.1 Adverse Events

Treatment-emergent AEs (TEAEs) are defined as any AEs, regardless of relationship to study drug, that have an onset or worsening in severity on or after the time/date of the baseline (dosing) visit (the reference date).

All descriptive statistics will be presented by dose level and all dose levels combined. Unless otherwise indicated, AE summaries will be presented by the following periods:

- Baseline through Week 24 (inclusive)
- >Week 24 through Week 48
- >Week 48 to End of Study
- Overall for the study

An overview table to report the number and percentage of participants and number of events will include the following:

- TEAEs,
- Drug related TEAEs,
- Serious TEAEs,
- Serious drug related TEAEs,
- TEAEs leading to withdrawal of study
- Drug-related TEAEs leading to withdrawal of study
- TEAEs leading to death,
- Drug related TEAEs leading to death,
- NCI-CTCAE Grade 3 or higher TEAEs
- NCI-CTCAE Grade 3 or higher drug related TEAEs
- Deaths

NCI-CTCAE v4.03 or higher will be used for assessment of grade.

The number and percentage of participants with TEAEs, as classified by SOC and PT will be summarized for each treatment group and overall. Summaries will be provided for the following:

- TEAEs
- Drug related TEAEs,
- Serious TEAEs,
- Drug related serious TEAEs,
- TEAEs leading to withdrawal of study,
- Drug related TEAEs leading to withdrawal of study,
- NCI-CTCAE Grade 3 or higher TEAEs,
- NCI-CTCAE Grade 3 or higher drug-related TEAEs,
- TEAEs leading to death,
- Drug-related TEAEs leading to death,
- Frequently reported ($\geq 10\%$ in All Dosed Group) TEAEs by preferred term,
- Frequently reported ($\geq 5\%$ in Any Treatment Group) TEAEs Excluding Serious TEAEs (this table will only be presented for the overall study duration)

Related AEs are those with relationship to study medication reported as “possible” or “related”. If relationship to study drug of an AE reported by treated participants is not recorded, the relationship will be imputed as “possibly related”, for analysis purposes. In the participant listing, both collected and imputed values will be presented.

An overview table to report number of events, and events adjusted by participant year from date of drug exposure (each summary classified by category below, SOC and PT) will include the following:

- Serious respiratory TEAEs,
- Serious non-respiratory TEAEs

In the participant count, if a participant has multiple TEAEs with the same SOC or PT, but with differing severity, relationship, or action taken, then the participant will be counted once with the worst nonmissing severity grade, highest degree of relationship, or highest severity of action taken (Not Applicable < Dose Not Changed < Drug Interrupted < Drug Withdrawn). If severity, relationship, or action taken is missing for all episodes of the event, the participant will be counted under missing severity, relationship, or action taken. This summary will only be created for the ‘overall’ period.

The following adverse events of special interest (AESI) are defined by the following categories and corresponding MedDRA Version 26.0 SMQ search criteria. If MedDRA Version is upgraded, then the search criteria will be correspondingly upgraded to align with the updates:

- **Muscle abnormalities**
 - Rhabdomyolysis/myopathy (SMQ, broad and narrow)
 - Investigations (SOC)

- Investigations, imaging and histopathology procedures (HLGT)
- **Myocarditis**
 - Noninfectious myocarditis/pericarditis (SMQ - broad)
- **Hepatobiliary disorders**
 - Hepatic Disorders (SMQ – broad)
 - Drug related hepatic disorders (SMQ - broad)
 - Cholestasis and jaundice of hepatic origin (SMQ - broad)
 - Drug related hepatic disorders - severe events only (SMQ - broad)
 - Liver related investigations, signs and symptoms (SMQ - broad)
 - Liver-related coagulation and bleeding disturbances (SMQ - broad)
 - Biliary disorders (SMQ - broad)
 - Functional, inflammatory and gallstone related biliary disorders (SMQ - broad)
 - Biliary system related investigations, signs and symptoms (SMQ - broad)
 - Biliary tract disorders (SMQ - broad)
 - Gallbladder related disorders (SMQ - broad)

The number and percentage of participants with AESIs, as classified by AESI category, SOC and PT will be summarized for each treatment group and overall. Summaries will be provided for the following:

- TEAEs
- Drug related TEAEs,
- Serious TEAEs,
- Drug related serious TEAEs,
- Grade 3 or higher TEAEs,
- Grade 3 or higher related TEAEs

Swimmer plots will be created, which will include information on glucocorticoid dosing (dose/duration) and AESI occurrence.

All AESIs will be listed.

All AEs that correspond to the MedDRA COVID-19 narrow SMQ search term will be listed separately.

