Clinical significance of out-of-range laboratory findings is to be determined and documented by the Investigator or Sub-Investigator who is a qualified physician. Abnormal laboratory findings associated with the underlying disease are not considered clinically significant unless judged by the Investigator to be more severe than expected for the subject's condition.

Laboratory abnormalities that are considered to be clinically significant by the Investigator must be recorded as AEs. Laboratory abnormalities (eg, clinical chemistry, hematology, coagulation parameters, and urinalysis) that require medical or surgical intervention must be recorded as an AE, as well as an SAE if the abnormality meets SAE criteria (defined in [Section 6.2.1](#)). In addition, laboratory or other abnormal assessments (eg, ECG, X-rays, vital signs) that are associated with signs and/or symptoms must be recorded as an AE or SAE if they meet the definition of an AE or SAE as described in [Sections 6.1.1](#) and [6.2.1](#), respectively. If the laboratory abnormality is part of a syndrome, record the syndrome or diagnosis (eg, anemia), not the laboratory result (eg, decreased hemoglobin).

The following laboratory abnormalities should be recorded as AEs regardless of whether considered to be clinically significant, unless the abnormality is considered to be part of an integrated diagnosis:

- Troponin I or Troponin T values above the ULN (or a non-zero value if no ULN is reported) for which additional diagnostic workup and/or treatment is indicated per consultation with the site pediatric cardiologist (see [Section 4.6.1](#))
- Platelet values below the lower limit of normal, or below the subject's baseline value if abnormal at baseline

Please contact the Medical Monitor if there are questions regarding how to capture laboratory abnormalities.

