6.5.3.1 Definition of Liver Abnormalities

For laboratory abnormalities (including liver) reported as AEs, severity grading assessment should follow the NCI-CTCAE (v4.03) Investigation system organ class.

In addition, the subject should be considered to have **severe hepatic abnormalities for any of the following:**

- ALT or AST > 8 × ULN
- ALT or AST > 5 × ULN for more than 2 weeks
- ALT or AST > 3 × ULN and* TBL > 2 × ULN or international normalized ratio (INR) > 1.5 (If INR testing is applicable/evaluated)
- ALT or AST > 5 × ULN and* TBL > 2 × ULN
- ALT or AST > 3 × ULN with the appearance of fatigue, nausea, vomiting, right upper quadrant pain or tenderness, fever, rash, and/or eosinophilia (> 5%)

* Samples taken simultaneously or within a maximum of 24 hours.

The Investigator may determine that abnormal liver function results, other than those described above, may qualify as moderate or severe abnormalities and require additional monitoring and follow-up.

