7.4.1.1 Adverse Events

AEs will be coded using the Medical Dictionary for Regulatory Activities (MedDRA) dictionary.

Events will be identified as treatment-emergent (TEAE) and non-treatment-emergent (non-TEAE) on the basis of the date of onset relative to the date of AT132 dosing.

Number and percentage of subjects with TEAEs classified by system organ class (SOC) and preferred term (PT); by severity, causality, seriousness, and action taken with regard to study drug will be summarized. Number (%) of subjects with TEAEs leading to discontinuation of study will also be summarized. Hospitalization will be summarized by frequency (%) and duration. TEAEs and/or hospitalizations may be annualized.

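### The muscle AESI in SAP 4.6.1 is searched with the unrestricted Investigations SOC, so non-muscle laboratory events can enter its by-dose totals

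*SAP*

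**What the plan says.** SAP Section 4.6.1 says that the AESIs "are defined by the following categories and corresponding MedDRA Version 26.0 SMQ search criteria". For muscle abnormalities it lists three items, each at the same level in the text available:

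- "Rhabdomyolysis/myopathy (SMQ, broad and narrow"
- "Investigations (SOC"
- "Investigations, imaging and histopathology procedures (HLGT"

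The SOC line carries no PT list, no exclusion and no restriction to creatine kinase (CK) or other muscle terms. The myocarditis and hepatobiliary categories are built from SMQs only, and the hepatobiliary list includes "Liver related investigations, signs and symptoms (SMQ - broad".

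The section then plans AESI summaries by category, SOC and PT, for each dose group and overall: all TEAEs, drug-related, serious, serious drug-related, and Grade 3 or higher (all and related). It also plans swimmer plots that show AESI occurrence together with glucocorticoid dosing, and a listing of all AESIs.

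**The concern.** Protocol Section 1.5 treats hepatobiliary, myocardial, muscle and platelet risks as separate identified risks. An AESI category is useful only if its count reflects the risk it is named for. A programmer who follows the muscle list literally would flag any AE in the Investigations SOC, whichever organ it concerns.

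The comparison at stake is the one the analysis now exists to describe. SAP Section 1.3 says the intent has become a description of safety and efficacy at the low and high dose. Protocol Section 1.4.2 names falling platelet counts and worsening of existing hyperbilirubinemia as possibly dose-related at the higher dose. If such events are recorded as laboratory terms and counted as muscle, the muscle category can show a dose gradient produced by the liver or the platelets.

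The swimmer plots are exposed in a particular way. Protocol Section 4.6.2.3 lets the investigator adjust prednisolone when liver tests rise. A liver laboratory event flagged as muscle would then appear beside a steroid change that it prompted, and could be read as a link between muscle events and steroid dosing.

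**Working it through.** The plan gives no figure to reproduce. The check sets the search definition beside the protocol's rules on recording AEs.

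**Step 1. Does the protocol generate laboratory-term AEs that are not muscle events?** Yes.

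- Protocol 6.3.1: a Grade 3 or 4 laboratory result that has worsened from baseline is reported as an AE unless it belongs to a diagnosis already reported.
- Protocol 6.4: two kinds of result are recorded as AEs whatever their clinical significance, unless part of an integrated diagnosis. One is a troponin above the ULN for which further workup or treatment is indicated. The other is "Platelet values below the lower limit of normal", or below the subject's own baseline if that was already abnormal.
- Protocol 6.5.3.2: severe liver function abnormalities are reported as SAEs.

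**Step 2. Would these code to the Investigations SOC?** The documents do not reproduce the MedDRA hierarchy, so this is an assumption. Protocol 7.4.1.1 says "AEs will be coded using the Medical Dictionary for Regulatory Activities (MedDRA) dictionary". The nearest support is Protocol 6.5.3.1: "For laboratory abnormalities (including liver) reported as AEs, severity grading assessment should follow the NCI-CTCAE (v4.03) Investigation system organ class". That sentence governs CTCAE grading, not MedDRA coding. It shows how the sponsor classes laboratory AEs, but does not prove where each one is coded.

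**Step 3. What limits the effect?** Protocol 6.4 asks for the syndrome or diagnosis in place of the laboratory result where there is one. Events recorded that way may code to another SOC and escape the search.

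**Step 4. Does the other reading of the SOC line remove the problem?** Suppose the line only names the parent of the HLGT below it. The search is then narrower, but the HLGT as named covers imaging and histopathology in general. The protocol schedules liver ultrasound and echocardiography (5.4, 5.5) and allows cardiac MRI and endomyocardial biopsy (4.6.1.3). Nothing in the SAP keeps abnormal findings from these out of the muscle category.

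**Step 5. Illustration of the dose pattern.** Protocol 1.4.2, data cutoff 08 July 2020: 5 subjects at the high dose had AT132-related hepatobiliary SAEs, in a cohort of 17. None of the 6 low-dose subjects did. Let k be the number of those 5 with at least one such SAE recorded as an Investigations laboratory term and no other event already placing them in the muscle row. The documents do not give k, so it runs from 0 to 5. The addition to the serious drug-related muscle row is k/17 at the high dose and 0/6 at the low dose:

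| k | High dose, k/17 | Low dose, 0/6 |
|---|---|---|
| 0 | 0.0% | 0.0% |
| 1 | 5.9% | 0.0% |
| 3 | 17.6% | 0.0% |
| 5 | 29.4% | 0.0% |

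The range covers one route and one cutoff. Protocol 1.5 later reports a low-dose death with hepatobiliary failure among its causes, so the final low-dose figure may not be zero. At least some of the five may have been recorded only as diagnoses, which would lower k.

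**The case against.** The strongest reply is that the SOC line is a hierarchy label. List nesting can be lost when a PDF is read as text. The HLGT's own name suggests it sits within Investigations, and it would be redundant if the whole SOC were searched. This is possible, but the SAP does not say it, and the introductory sentence presents the listed items as the search criteria. Step 4 shows that this reading narrows the problem without removing it.

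Second, the harm is bounded. The AESI tables are broken down by SOC and PT, all AESIs are listed, and laboratory thresholds, CTCAE shifts and liver criteria are summarized separately (SAP 4.6.2.1, 4.6.2.2). A careful reader could pick out the non-muscle terms. This stands: it would be wrong to infer that the muscle table tells the reader nothing. What is affected is the category-level count in each row and the plot flags.

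Third, the SAP version history says the AE definitions were aligned to the Investigator's Brochure, which is not available here. This also stands, and any replacement list should be checked against it.

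Fourth, the SAP does not claim that AESI categories are mutually exclusive, so one event in two categories is not in itself an error. That is correct, but the plan should say so.

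**Conclusion.** The muscle AESI definition is wrong as written and should be corrected. Applied literally, it admits any AE coded to the Investigations SOC. On the parent-label reading it is unclear and still not confined to muscle. The consequence is inflated muscle totals, serious and Grade 3 or higher rows and swimmer-plot flags, with the possibility of a spurious dose pattern. The analysis is descriptive (SAP Section 2), so no error rate is affected.

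The conclusion assumes that at least some liver, troponin or platelet AEs were recorded as laboratory terms and coded to Investigations. The documents make this likely but give no count. The 0 to 29.4 point range in the working is an illustration, not an estimate.

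Two stronger readings are not supported:

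- A reader might infer that nearly every treated child would be flagged, because Protocol 1.5 calls troponin and CK rises common. Those statements describe laboratory values, not recorded AEs, and give no counts. CK is also a muscle marker and belongs in the category.
- A reader might see a parallel fault in the hepatobiliary list, which appears to name broad SMQs alongside their components. Overlapping criteria within one category form a union and add no participant.

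**What to change.** In SAP 4.6.1, before database lock:

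- Remove the Investigations SOC as a stand-alone criterion for muscle abnormalities.
- Keep the rhabdomyolysis/myopathy SMQ.
- Limit any terms taken from Investigations or the named HLGT to a prespecified list of muscle-related PTs, for example CK terms and abnormal muscle biopsy, muscle MRI or EMG findings, checked against the Investigator's Brochure.
- If the SOC line was meant only as the parent of the HLGT, say so, and restrict the HLGT to the same list.
- State that an event may count in more than one AESI category.

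The cost is a few lines of SAP text, a PT list with medical review, and an update to the AESI flag in programming. No new data are needed.
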